- 5.4. Data Recipient's obligations under Articles III and IV and Sections 5.7, 5.9 and 5.11 of this Agreement shall survive the termination of this Agreement.
- 5.5. If any provision of this Agreement is determined by a court of competent jurisdiction to be invalid, void, or unenforceable, the remaining provisions shall continue in full force and effect.
- 5.6. This Agreement shall be governed by the laws of the State of Oregon.
- 5.7. The Data Recipient shall indemnify, defend, and hold OCHIN harmless from and against any actual legal or administrative action, claim, liability, penalty, fine, assessment, lawsuit, litigation, or other loss, expense, or damage, including without limitation any reasonable attorneys' fees and costs that OCHIN may incur directly or indirectly resulting from any actions or omissions of Data Recipient, its agents or subcontractors, including failure to perform its obligations under this Agreement.

- 5.8. OCHIN shall indemnify, defend, and hold Data Recipient harmless from and against any actual legal or administrative action, claim, liability, penalty, fine, assessment, lawsuit, litigation, or other loss, expense, or damage, including without limitation any reasonable attorneys' fees and costs that Data Recipient may incur directly or indirectly resulting from any actions or omissions of OCHIN, its agents or subcontractors, including failure to perform its obligations under this Agreement.
- 5.9. Data Recipient shall obtain and maintain during the term of this Agreement liability insurance covering claims based on a violation of HIPAA or any applicable state law or regulation concerning the privacy of patient information and claims based on its obligations pursuant to this Agreement in an amount not less than \$1,500,000 per claim. Such insurance shall be in a form of occurrence based coverage. A certificate evidencing the policy shall be provided to OCHIN upon written request. Data Recipient shall provide OCHIN at least thirty (30) days' advance notice of cancellation or material modification to said policies.
- 5.10. This Agreement, including all Attachments and Exhibits which are deemed incorporated by this reference, is the entire Agreement between the parties, and no other agreements, oral or written, have been entered into with respect to the subject matter of this Agreement. This Agreement specifically supersedes and replaces all prior agreements between the parties on the subject matter of this Agreement whether oral or written.
- 5.11. Data Recipient shall not assign its rights, duties or obligations under this Agreement (including by merger, consolidation, or acquisition) without the prior written consent of OCHIN. OCHIN may assign this Agreement to any affiliate, subsidiary, parent or related entity of OCHIN.
- 5.12. No term or provision of this Agreement shall be deemed waived and no breach excused unless waiver or excuse of breach is in writing and signed by the party against whom such waiver or excuse is claimed.

IN WITNESS WHEREOF, the parties have executed this Agreement effective as of: _____

OCHIN, Inc.	
By: 	By: 
Name: [name]	Name: [name]
Title: Chief Executive Officer	Title: Associate Vice President, Office of Proposal & Award Management
Date: 4-6-16	Date: March 28, 2016:

EXHIBIT A to the Data Use Agreement for Research
By and Between OCHIN Inc. and Oregon Health & Science University (OHSU)
on behalf of the OHSU Department of Family Medicine
Dated 1/ 15/ 2016

1. Description of the Study, including description of the project goals and objectives and the relationship of the Study to the interests of OCHIN members:

This study, *Post Affordable Care Act: Evaluation of Community Health Centers*, proposes to examine the impact of the Affordable Care Act (ACA) Medicaid expansion on patients utilizing community health centers (CHCs). The Supreme Court ruling, which determined that states were not legally required to implement the ACA Medicaid expansion, created a 'natural policy experiment.' We will use electronic health data from the national ADVANCE clinical data research network (CDRN), which has patient-level data in expansion and non-expansion states, to measure pre-post expansion health care utilization, receipt of services, and Medicaid expenditures.

The specific aims of this proposal are: 1) Compare pre-post health insurance status, primary care, mental health, and dental visits, and receipt of preventive services, as well as changes in payer mix among CHCs in states that did and did not expand Medicaid; 2) Examine pre-post utilization of CHC services (including receipt of preventive services) by newly insured compared to already insured and uninsured patients; and 3) measure pre-post changes in overall utilization of healthcare services and Oregon Medicaid expenditures among newly insured compared to already insured patients.

The research will be informed by an Expert Advisory Group of local and national experts who will meet quarterly, including: [name], a CHC patient and founding member of OCHIN's patient engagement panel; [name], PhD, a health services researcher and state legislator; [name], MPH, a Principal at Health Management Associates; [name], the medical director of CareOregon, an Oregon-based, non-profit, Medicaid health plan; and [name], MS, RN, Washington County (Oregon's second largest county) Health and Human Services Director. This study will have national relevance, as it measures how Medicaid expansion impacts access and changes in receipt of health care services among vulnerable populations.

2. Limited Data Set. The Limited Data Set will contain the following variables and/or variables that have been derived from these variables (such as counts, means, etc.) ("Data Elements"):

DATA ELEMENTS– LIMITED DATA SET

DATA ELEMENTS:

The data included in the datasets will fall into several classes as shown in the table below. Some examples of each class of data are shown but do not comprise an exhaustive list of possible variables to be included in the dataset.

ADVANCE Tables	Examples include, but are not limited to:
Demographics	Patient id, sex, date of birth, race, ethnicity, primary language, annual income, FPL, primary payor, state of residence, sites
Enrollment	Patient id, site id, enrollment start date, enrollment end date
Encounter	Encounter id, patient id, admit date, provider id, facility location, encounter type, facility id, admitting source, primary payor, site id
Diagnosis	Diagnosis id, patient id, encounter id, encounter type, admit date, provider id, diagnosis, diagnosis type, diagnosis source, site id
Procedures	Procedures id, patient id, encounter id, encounter type, provider id, procedure date, procedure code, procedure type, procedure source, site id

7

Vital	Vital id, patient id, encounter id, measure date, measure time, vital source, height, weight, diastolic blood pressure, systolic blood pressure, original bmi, blood pressure position, smoking, tobacco, tobacco type, site id
Dispensing	Dispensing id, patient id, prescribing id, dispense date, national drug code, dispense supply, dispense amount, site id
Lab Result CM	Lab result cm id, patient id, encounter id, lab name, specimen source, lab LOINC, result location, lab procedure, lab procedure type, lab order date, result date, result quality, result number, result modifier, result unit, norm range low, norm range high, norm modifier high, abnormal result indicator, site id
Condition	Condition id, patient id, encounter id, report date, onset date, resolve date, condition status, condition, condition type, condition source, site id
Prescribing	Prescribing id, patient id, encounter id, rx provider id, rx order date, rx start date, rx end date, rx quantity, rx refills, rx days supply, rx frequency, rx basis, rx norm concept identifier, site id
Death	Patient id, death date, death date imputed, death source, death match confidence, site id
Death cause	Patient id, death cause, death cause code, death cause type, death cause confidence, site id

3. **Time Period.** The Limited Data Set includes Data Elements for the following time period: 1/1/2012 to 12/31/2017

4. **OCHIN Members.** Data Elements from the following OCHIN members are included in this Limited Data Set:

AH FEATHER RIVER HC	COMMUNITY HEALTHNET	INCLINE MEDICAL	METROPOLITAN COMMUNITY HEALTH
ALLIANCE MEDICAL CENTER	COWLITZ FAMILY HEALTH CENTER	ONE COMMUNITY HEALTH	MOLINA MEDICAL MANAGEMENT
AXIS MEDICAL CENTER	CROOK COUNTY	THE NATIONAL COLLEGE OF NATURAL MEDICINE	MONTEREY COUNTY HEALTH DEPT
BASTYR UNIVERSITY	OHSU	JEFFERSON COUNTY HEALTH DEPT	CLINICA ROMERO
BENTON HEALTH SERVICES	DESCHUTES COUNTY HEALTH DEPT	KODIAK COMMUNITY HEALTH CENTER	NORTHERN HEALTH CENTERS
CARE ALLIANCE	DUNES FAMILY HEALTH	LAGUNA BEACH COMMUNITY CLINIC	MOSAIC MEDICAL
CARING HEALTH CENTERS	OUTREACH COMMUNITY HEALTH CENTER	LINCOLN COUNTY HHS	MULTNOMAH COUNTY HEALTH DEPT
CHC OF CAPE COD	EL CENTRO DE CORAZON	LYNN COMMUNITY HEALTH CENTER	COASTAL FAMILY HEALTH CENTER

CLACKAMAS COUNTY PHD	FREE CLINIC OF CLEVELAND	MERCY CARE	QUEENSCARE HEALTH CENTERS

For projects that are primarily research, you must submit your *IRB* application accompanied by the signed, dated approval. If you have any question about what constitutes research, please contact the Manager of Health Programs Analysis and Measurement Unit.

RESEARCH APPLICATION

Please use this template to fill in your information

Applicant Name: OCHIN, Inc.

Applicant Address: [name]

Applicant Contact Name: [name], DPhil, [contact], [contact]

1. Describe the general purpose of study.

The purpose of the “*Long-term Trends in Health Insurance Coverage and Access to Health Care Services*” study is to understand trends in health insurance coverage and access to health care services over time in a safety net population. This will include investigating health insurance coverage patterns and differences in health insurance coverage reported in OCHIN versus the Oregon Health Plan [(OHP) Oregon’s Medicaid Program]. We will look at health care services patients receive and how health insurance coverage impacts these services. Additionally, we will look at how health insurance patterns and health care services change as state and federal policies are implemented (for example, the Affordable Care Act, or Coordinated Care Organizations) in Oregon as well as the other states with OCHIN clinics. We will also compare the use of electronic health record tools to keep patients insured.

2. Describe the specific details of the request:

a. Detail the purpose of request, state the research or evaluation question(s), hypotheses to be tested:

This study will 1) examine the relationship between health insurance coverage and receipt of health care services, alone and in relation to policy change, 2) track changes in health insurance patterns and health care services, alone and in relation to policy change, 3) assess differences between OCHIN and DMAP data, and 4) evaluate the use of electronic health record tools to keep patients insured.

b. Specify the data elements/information that is requested from DMAP, which enrollment and claims data elements for specific date periods:

This is a secondary data analysis study only. Potential subjects will be from four OHSU IRB-approved research studies for which there already exist individual Data Access Agreements with OHA DMAP [IMPACCT (OHSU IRB#00009244, OHA Request #2653), FAMILY (OHSU IRB#00006727, OHA Request #2398), AMRIC (OHSU IRB#00007327, OHA Request #2545), and CATCH UP (OHSU IRB# IRB00009862; OHA Request #3455)].

To meet the aims of this study, we will utilize all Claims data (inpatient/long-term care, outpatient, and pharmacy claims); Eligibility/Enrollment data (including demographic variables); and Provider Information data (including but not limited to

provider ID and provider type) for the period 1/1/2002-6/30/2019, for all children (ages 0-20) and adults (ages 18 and older).

We would like to utilize data currently being received under the auspices of the four studies mentioned above. In addition, we are now requesting some additional data to fill in the gaps in the existing DMAP data for the timeframe of the “Long-term Trends in Health Insurance Coverage and Access to Health Care Services” study.

Specific additional data we are now requesting include:

- Inpatient claims, 2002-2010, ages 0-20
- Eligibility/enrollment, outpatient claims, and pharmacy claims, 2002-2010, ages 19-20
- All files, 2002-2004, ages 18+
- All files, 2013-6/30/2019, all ages
- Language and ethnicity demographic elements for all years, all patients
- Primary care home data for CCO patients, all applicable years

We request receipt of the data currently available, with the remainder provided separately when it becomes available and on a schedule mutually agreed upon by OCHIN Inc. and Oregon Health Authority, Division of Medical Assistance Programs (DMAP).

c. Details of how DMAP data will be used for said purpose:

Our analyses will include: 1) descriptive examinations of the data, including demographics, characterization of variations and patterns of insurance coverage, and receipt of health care alone and in relation to policy changes. Insurance coverage may be displayed on maps to visualize areas where uninsurance rates are higher; 2) analyses of how factors are associated with outcomes of interest; 3) examination of various lag times for gain / loss of insurance coverage and changes in utilization patterns; 4) identification of potential confounders; and 5) evaluation of the impact of insurance coverage status change / no change on utilization of preventive services, adjusted for potential confounders. We will also assess the interaction between insurance status and continuity of coverage.

d. Provide the names and contact information for lead or principle investigators and any others who have access to data information we provide:

[name], DPhil	OCHIN	[contact]
[name]	OHSU	[contact]
[name]	OCHIN	[contact]
[name], BA	OHSU	[contact]

[name], MPH	OHSU	[contact]
[name]	OCHIN	[contact]
[name]	OHSU	[contact]
[name]	OCHIN	[contact]
[name]	OHSU	[contact]
[name]	OHSU	[contact]
[name], MS	OHSU	[contact]
[name], RN	OCHIN	[contact]
[name]	OCHIN	[contact]
[name], MA	OCHIN	[contact]
[name]	OHSU	[contact]
[name]	OHSU	[contact]
[name]	OHSU	[contact]
[name]	Kaiser Permanente CHR/OCHIN	[contact]
[name]	State of Oregon	[contact]
[name], MID, MPH	OHSU	[contact]
[name]	OHSU	[contact]

e. Specifics on how the purpose helps DMAP administer the Medicaid program: and,

The proposed project could result in expanded understanding of health services DMAP covered children and adults receive at Community Health Centers (CHCs) and how health insurance coverage impacts these services, alone and in relation to policy changes. In addition, this project could result in better understanding of how the use of electronic health record tools to keep patients insured affects continuity of coverage. These tools have potential for widespread adoption in CHCs providing care

to DMAP covered children and adults. Increased continuity of coverage could improve the quality of evidence-based care provided to the CHC patients and reduce administrative burden associated with "churning".

f. Timeframe of study. 1/1/2002 to 06/30/2019

NOTE: Access to DMAP's data will only be granted if the purpose supports the administration of the Oregon Health Plan. The request must detail how the data supports the administration of the Oregon Health Plan. Purpose statement must also support each specific data element requested.

- 3. Detail the administrative, technical, and physical safeguards Requestor will use to protect the data set.** Specifically, in order to ensure that client privacy is protected and meets DHS' Health Insurance Portability and Accountability Act Of 1996, (HIPAA) privacy policies, review and agree to abide by the OHA administrative policies including:

Administrative, Technical and Physical Safeguards Policy	OHA-100-005
Client Privacy Rights Policy	OHA-100-002
De-identification of Client Information and Use of Limited Data Sets Policy	OHA-100-007
Enforcement, Sanctions and Penalties for Violations of Individual Privacy Policy	OHA-100-009
General Privacy Policy	OHA-100-001
Minimum Necessary Information Policy	OHA-100-004
Uses and Disclosures of Client or Participant Information Policy	OHA-100-003
Uses and Disclosures for Research Purposes and Waivers Policy	OHA-100-006

(See <http://www.oha.state.or.us/policy/admin/privacypolicylist.htm>). Ensure that the description meets Title II, Subtitle F of the Health Insurance Portability and Accountability Act of 1996, 42USC 1320d et.seq, and, when applicable, the Substance Abuse and Mental Health confidentiality regulations outlined in Part II of the Department of Health and Human Services, Public Health Service, 42CFR Part 2; ORSs 179.505, 192.535, 192.547.

- 4. Provide a detailed description of health information safety and privacy protocols.** Under the current business associates agreement between OCHIN and DMAP, DMAP will provide OCHIN with a file containing the requested data.

All data exchanges will be done using standard security processes with password-controlled Secured File Transfer Protocol (SFTP) access. Access will be given only to study personnel. All reports will describe results in aggregate form only.

OHSU will receive the data once the following identifiers are removed: OHP and OCHIN ID numbers, names, full addresses, and phone numbers. IRB approval has been obtained from this research at OHSU. OCHIN has requested OHSU be the IRB of record for this study.

(Agreement / Request # 3524)

INFORMATION ACCESS AGREEMENT

This agreement is between the Oregon Health Authority, Division of Medical Assistance Programs (DMAP),

and **OCHIN, Inc.**
[name]
[name], DPhil, [contact], [contact] OCHIN, Inc.,
here forward known as "Requestor" has requested access to DMAP's:

Claims data (inpatient/long-term care, outpatient, and pharmacy claims); Eligibility/Enrollment data (including demographic variables); Provider Information data (including but not limited to provider ID and provider type) for the period 1/1/2002-6/30/2019, for all children (ages 0-20) and adults (ages 18 and older).

Requestor of information related to Fee-for-Service medications will agree to use it specifically and exclusively as stated in the Information Access Agreement and in the attached Research Application. Additionally, as a condition of use and for an extension of the agreement, the requestor will provide DMAP a documentation of how this information was used to meet the terms of this agreement, upon request.

Requestor warrants and agrees:

1. The confidentiality of all data sources used for the purposes stated above will be protected as mandated by state and federal laws and regulations, including HIPAA privacy regulations; and that all information related to personal facts and circumstances of DMAP will be treated as privileged communications and will be held confidential;
2. Any data provided by DMAP will not be physically moved or electronically transmitted unless written authorization is received from DMAP; if the above stated purpose or security protocols outlined above includes electronic transmission or physical movement of data, this Agreement serves as such written authorization for only above-stated purpose and specifications;
3. That the facts and statements made above in any research protocol, study, or project plan submitted to DMAP for each purpose are complete and accurate;
4. That the data will not be used for any other purposes other than those stated above unless upon mutually agreed between Requestor and DMAP with written authorization by authorized DMAP representative;

5. That any information related to behavioral health patient records will be treated with the federal and state standards for confidentiality as defined in Part II of the Department of Health and Human Services, Public Health Service, 42CFR Part 2; and ORS 179.505;
6. That no findings, listing, or information derived from the file(s) and data will be released or disclosed to other parties with or without identifiers, if such findings, listing, reports, or information contain any combination of data elements that might allow the deduction of a beneficiary's identification, without first obtaining written authorization from the appropriate DMAP representative (see DMAP signatory below);
7. That access will be limited to individuals directly involved and identified that are necessary to achieve the purposes stated above, and that access will be limited to the minimum amount of data necessary to achieve the purpose stated above, and that any breach of security or violations to this agreement will be reported to DMAP as soon as you are aware of the violation;
8. That the Requestor has in place appropriate administrative, technical, and physical safeguards so that DMAP data will be protected to prevent unauthorized use, and that authorized DMAP representative will be granted access to premises where above-stated data are kept for the purpose of inspecting security arrangements to confirm that the Requestor is in compliance with security requirements;
9. That data will be destroyed and an attestation shall be provided to that effect or the data will be returned not later than 60-days after completion of the project as specified above, unless written agreement between Requestor and appropriate DMAP representative. Requestor will notify DMAP within 30-days of completion of project date once above stated purpose has been accomplished, if completed before above-stated completion date. Requestor will submit, on Requestor's letterhead, confirmation that no copy, data, nor parts thereof have been retained, and that the data has been destroyed or has been returned. Said letter (and returned data) should be sent to DMAP's address on first page of the Agreement. The data agreement must be reviewed and resubmitted no less than annually if research project extends beyond one year. The ability of the Requestor to use the data under this agreement is valid for one year and must be extended in writing;
10. That DMAP will be consulted in the analysis of the data and interpretation of the results, and be allowed reasonable time to review for accuracy any reports or published articles from this study prior to release.

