Methods to account for non-users in the post-period. The available data do not indicate whether patients without clinic contact in the post-period are true non-users, or drop-outs (*i.e.*, left the clinic permanently to seek care elsewhere), potentially leading to underestimated utilization rates. A dropout rate that is similar across groups will not impact the comparison between clinics in expansion versus non-expansion states or between patients with different coverage status, but differential dropout poses a threat to the generalizability of the findings. As a sensitivity analysis, we will use pre-expansion data to model the probability that a patient has a visit in year t based on demographic information and the number of visits to the clinic in year $t-1$ and $t-2$. Parameters from this model will be used to attach a weight to all patients across all years. This method provides a measure of the contribution of each patient on utilization measures and avoids bias that may arise from defining patient attribution according to utilization patterns that occur because of the Medicaid expansion.

Standard errors adjustments. Depending on the distribution of the outcomes of interest, standard errors may be difficult to estimate using standard regression variance output. Thus, we plan to implement bootstrapping to obtain reliable standard errors when appropriate. Additionally, as a sensitivity analysis, we plan to bootstrap all analytic models simultaneously to allow estimating covariances among parameter estimators across models.

Power calculations. For **Aim 1**, our total sample size includes 761,840 patients distributed over

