ADVANCE EHR Data. We used electronic health record (EHR) data from the Accelerating Data Value Across a National Community Health Center Network (ADVANCE) clinical data research network (CDRN) data warehouse. The ADVANCE CDRN is a unique ‘community laboratory’ for research with underrepresented populations that includes patients receiving care in safety net clinics. The ADVANCE CDRN data warehouse includes *integrated* longitudinal EHR data from several organizations. Data from two ADVANCE partners, OCHIN and Health Choice Network (HCN), were used in the PACE study. From the ADVANCE CDRN, we included CHC members ‘live’ on their EHR as of January 1, 2013: 225 primary care CHCs in 10 states that expanded Medicaid as of 1/1/2014 (California, Hawaii, Maryland, Minnesota, New Mexico, Ohio, Oregon, Rhode Island, Washington, and Wisconsin) and 134 primary care CHCs in 6 non-expansion states (Florida, Kansas, Missouri, North Carolina, Texas, Montana). We included Wisconsin as an expansion state because although they did not expand Medicaid to 138% FPL they opened enrollment to adults with eligibility criteria of 100% FPL and therefore behaved more like an expansion state. Montana did not expand Medicaid until after our study period (expanded 1/1/2016), which included a one-year pre- (1/1/13-12/31/13) and a two-year post-period (1/1/2014-12/31/2015). Analyses included >4 million ambulatory visits among patients aged 19-64 (expansion states: 2.6 million visits from 499,719 patients; non-expansion states: 1.5 million visits from 370,600 patients).

Linkage between EHR and Medicaid administrative data. Oregon Medicaid administrative data was linked to OCHIN Oregon clinics in the ADVANCE CDRN to assess the receipt of healthcare services outside the Oregon CHCs and all healthcare expenditures.

Study Population and Study Period

The overall study population was adults ages 19-64 throughout the study period, 2012-2015. Included patients had ≥ 1 ambulatory visit at an eligible facility in the study period. Included facilities provided adult primary care and were ‘live’ on OCHIN’s or HCN’s EHR system by the start of the study period (1/1/2012). EHR data were extracted on all eligible patients, encounters, and facilities.

Overall, study analyses included >4 million ambulatory visits among patients aged 19-64 (expansion states: 2.6 million visits from 499,719 patients; non-expansion states: 1.5 million visits from 370,600 patients).

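### The SAP says its data cannot tell true non-users from drop-outs, but linked Oregon Medicaid data can for enrolled months, and the planned weight cannot identify leaving caused by expansion

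*Combined protocol and SAP*

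**What the plan says.** The SAP paragraph on non-users in the post-period (B.4.4) covers all three aims. It states: "The available data do not indicate whether patients without clinic contact in the post-period are true non-users, or drop-outs". It accepts that drop-out differing between groups is a threat. The sensitivity check it plans is this: "we will use pre-expansion data to model the probability that a patient has a visit in year t based on demographic information", together with the patient's visit counts in the two preceding years. Then: "Parameters from this model will be used to attach a weight to all patients across all years". The stated merit is that this "avoids bias that may arise from defining patient attribution according to utilization patterns that occur because of the Medicaid expansion".

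Other parts of the documents describe what is known about Oregon patients:

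- The combined document's paragraph on linking EHR and Medicaid data says the Oregon linkage was made "to assess the receipt of healthcare services outside the Oregon CHCs and all healthcare expenditures". The study design section of the appended IRB protocol says the same in substance.
- Table 3 of the combined document lists an agreement dated 6-20-16 that lets OCHIN use state-owned Medicaid data.
- The SAP makes use of services outside the CHCs a primary dependent variable of Aim 3.
- The Research Application to the Oregon Medicaid agency, item 2b, says: "we will utilize all Claims data (inpatient/long-term care, outpatient, and pharmacy claims); Eligibility/Enrollment data (including demographic variables); and Provider Information data".
- Exhibit A of the data use agreement includes a death table: "Patient id, death date, death date imputed, death source, death match confidence, site id".

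SAP B.4.6, item 2, separately anticipates patients who obtain care outside the network. It plans missingness covariates, multiple imputation and a comparison of completers with all patients.

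**The concern.** A patient with no CHC contact after January 2014 has either used no care or gone elsewhere. These mean different things for the newly versus already insured contrast in CHC visits (Hypothesis 2, part a) and for the CHC part of Hypothesis 3a. If gaining Medicaid leads more of the newly insured to take their care elsewhere, their CHC visit rate falls with no fall in use of care.

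The SAP treats the two states as inseparable everywhere and relies on a weight that by design ignores behaviour caused by the expansion. That is the behaviour behind the differential drop-out it fears. In Oregon, the data that would separate the two are linked for another purpose, and no section applies them to this question.

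**Working it through.** The documents give no drop-out rate, so there is no planned figure to reproduce. All leaving rates below are assumptions.

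**1. What Oregon data can show.** Both groups in the contrast are defined by Medicaid: gaining it, or already having it (combined document, study population). While enrolled after expansion, both are therefore visible in claims. The linkage was used: the EHR coverage-accuracy analysis covers 135,514 patients from 184 Oregon CHCs linked to state Medicaid records for 2013–2014.

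**2. Oregon's weight in the study.**
- Aim 3 sample relative to Aim 2: 187,684 / 447,488 = 41.9%.
- Table 2, patients in listed expansion states: 261,166 / 647,831 = 40.3%. With Wisconsin added: 261,166 / 668,424 = 39.1%.

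**3. How much leaving matters.** If a fraction x more of the newly insured leave, and a retained patient has probability p of any CHC visit in the year, the false difference is x·p. Setting x·p to the SAP's detectable difference for Aim 3 (2.8 points, 90% power, ICC 0.10) gives x = 2.8/p:

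| p (assumed) | 0.4 | 0.5 | 0.6 | 0.7 | 0.8 |
|---|---|---|---|---|---|
| x | 7.0% | 5.6% | 4.7% | 4.0% | 3.5% |

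**4. Effect on a visit rate ratio.** With no true effect, DID ratio = (1 − d_new)/(1 − d_already).
- 10% v 5%: 0.90/0.95 = 0.947
- 15% v 5%: 0.85/0.95 = 0.895
- 25% v 5%: 0.75/0.95 = 0.789

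**5. Does the planned weight help?** The simulation had 400,000 patients, a mean of 2 visits a year, no true effect and leaving at the start of 2014. A logistic model for any visit was fitted on pre-expansion years, and its parameters were carried forward. The SAP does not say how the weight enters, so two forms were tried with yearly updated lags.

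| 15% v 5% leaving | 2014 | 2015 | 2016 |
|---|---|---|---|
| Unweighted | 0.895 | 0.895 | 0.895 |
| Weight = predicted probability, updated lags | 0.895 | 0.917 | 0.953 |
| Inverse of that weight | about 0.90 | 0.876 | 0.824 |

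At 25% v 5%, the 2016 values are 0.788, 0.895 and 0.669. In 2014 both lags are pre-expansion, so leaving cannot enter the weight. From 2015 the lags contain post-expansion visits and the estimate moves, toward or away from 1.00 according to the form of the weight. No value is corrected.

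**6. The same check on the any-visit scale.** This used N = 187,684, no true effect, and 5.6% leaving among the newly insured only. Compare shifts, because the level without leaving carries sampling noise.
- 2014 unweighted: +0.66 to −3.17, a shift of −3.83 points.
- 2014 weighted: +0.66 to −3.40, a shift of −4.06. The newly insured's mean weight was 0.6872 with or without leaving.
- 2016 unweighted: −0.02 to −3.77, a shift of −3.75.
- 2016 weighted: −0.14 to −2.58, a shift of −2.44.
- In 2016, leavers and true non-users with no visits in the two lag years had nearly equal weights (0.41 v 0.40).
- Counting outside use returned the DID to its no-leaving values (+0.66 and −0.02). This assumes that claims capture all outside care.

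**7. A remedy that fails.** One could remove patients with outside claims from the denominator after their last CHC contact. With no leaving, no effect, and assumed occasional outside use of 0.6 v 0.3 a year over two years, that rule gives a false rate ratio of 1.11 (1.10 if a gap of at least 180 days is required). At 0.5 v 0.3 it gives 1.07.

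**The case against.** **Scope.** For patients outside Oregon, for the uninsured group of Aim 2 and for care paid by other sources, the SAP sentence is correct. This stands. A Decision Log entry of 06/16/16 also counts continuous private coverage as continuously insured, and such patients would not appear in Medicaid claims. Enrolment is often broken or out of scope: 230,602 of 622,513 Oregon adults (37%) remained in one analysis after its continuous-coverage and other exclusions.

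**Source.** The Research Application concerns a differently titled study with subjects from four other studies, and a request is not receipt. This stands for that passage alone. The linkage paragraph, Table 3, the Aim 3 outcomes and the coverage-accuracy analysis carry the point for PACE.

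**Other checks.** A reader might infer that the weight is the only safeguard. It is not, since B.4.6 adds covariates, imputation and a completer comparison. None of these uses claims to separate the two groups.

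**The weight as false reassurance.** A reader might infer that it returns the same biased answer however it is applied. That holds only in the first post year, or if the weights are frozen at pre-expansion values. With updated lags the estimate moves, and the movement could serve as a warning. What stands is that the weight neither identifies nor removes the leaving.

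**Estimand.** Hypothesis 2 is about CHC visits. If coverage leads patients away from CHCs, fewer CHC visits are part of the effect. This is fair, and it is why the CHC-visit DID should be kept and set beside total use. The SAP itself calls differential drop-out a threat, so it does want the two separated.

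**Conclusion.** The point holds for Oregon Medicaid-enrolled months. There the SAP's blanket statement conflicts with the project's own linkage. The planned weight cannot identify or remove leaving caused by expansion: the first post year is about equally biased with or without it, and in later years the estimate shifts without being corrected. An excess leaving rate of 3.5% to 7.0% would by itself produce a false difference equal to Aim 3's stated detectable difference, for retained visit probabilities of 0.8 down to 0.4.

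The leaving rates and their direction are assumptions, so the documents do not show that the Aim 2 or Aim 3 contrasts are in fact biased. Nor do they support the wider readings that non-users and drop-outs can be separated across the whole study, or that an Oregon leaving rate holds in other states. A claim elsewhere shows outside use; it does not prove permanent departure.

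**What to change.** 1. Limit the SAP sentence on indistinguishable non-users to EHR-only analyses.
2. For Oregon patients, take those with no CHC contact in a fixed post-period interval, for example a calendar year. Class them from linked enrolment and claims as enrolled with ambulatory claims elsewhere, enrolled with no claims, or not enrolled or deceased. Report the shares for newly versus already insured.
3. As a sensitivity analysis for Aim 3 and the Oregon part of Hypothesis 2a, present the CHC-visit DID alongside post-period total ambulatory use (CHC plus external) over all enrolled months. The newly insured have no pre-period Medicaid claims, so the total-use comparison is post-period only.
4. Do not end person-time at the last CHC contact.
5. Treat any use of the Oregon shares for other states as a labelled scenario only.

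The cost is a wording change and one more analysis of linked data. It is informative only for Oregon Medicaid-enrolled months and gives nothing for the uninsured group or other states.
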